11.4. Pharmacokinetic Analyses

Serum guselkumab concentrations at specified visits will be summarized by efficacy response status.

Descriptive statistics, including arithmetic mean, SD, median, interquartile range, minimum, and maximum will be calculated at each sampling time. All concentrations below the lowest quantifiable sample concentration of the assay (BQL) or missing data will be labeled as such in the concentration data listing or statistical analysis system dataset. The BQL concentrations will be treated as zero in the summary statistics.

If data permit, the relationships between serum guselkumab concentration and efficacy or serum biomarker level may be analyzed graphically.

11.5. Biomarker Analyses

Biomarker samples outlined in Section 9.4 will be used to define serum markers, skin gene expression and cellular profiles for correlation analyses to better understand:

- 1.) The mechanism of action and the molecular effects of guselkumab
- 2.) The pathogenesis of psoriasis including the differences between >2 years and ≤ 2 years disease duration
- 3.) Inter-individual variability in clinical outcomes

Furthermore, population subgroups may be identified who respond differently to guselkumab.

These analyses are considered exploratory and will be summarized in a separate technical report.

Planned biomarker analyses may be deferred if emerging study data show no likelihood of providing useful scientific information.

11.6. Pharmacogenomic Analyses

Pharmacogenomic analyses may include candidate gene analyses or genome-wide association analyses in relation to treatment response, maintenance of response, relapse, and non-response.

These analyses are considered exploratory. Details of the analysis plan and summary of results from pharmacogenomics analyses will be reported separately.

11.7. Safety Analyses

Safety data, including but not limited to, AEs, SAEs, infections, serious infections, changes in laboratory assessments, and changes in vital signs will be summarized. Treatment-emergent AEs (TEAEs) will be summarized by treatment group and Medical Dictionary for Regulatory Activities (MedDRA) system organ class (SOC) and preferred terms (PT).

Analysis Data Set

The safety analyses will be performed separately for each Study Part. For all safety analyses, all subjects treated with at least one dose of study drug will be included. For all the safety analyses, subjects will be analyzed according to the treatment they actually received.

Adverse Events

The verbatim terms used in the eCRF by investigators to identify AEs will be coded using MedDRA. All reported AEs with onset during the treatment phase (ie, treatment-emergent AEs, and AEs that have worsened since baseline) will be included in the analysis. For each adverse event, the percentage of subjects who experience at least 1 occurrence of the given event will be summarized by treatment group.

Summaries, listings, datasets, or subject narratives may be provided, as appropriate, for those subjects who die, who discontinue treatment due to an adverse event, or who experience a severe or a serious AE.

The following analyses will be used to assess the safety of subjects in the study:

- The incidence and type of AEs.
- The incidence and type of SAEs.
- The incidence and type of infections.
- The incidence and type of reasonably related AEs.
- The incidence and type of injection site reactions.
- The laboratory parameters and change from baseline in laboratory parameters (hematology and chemistry).

Clinical Laboratory Tests

Laboratory data will be summarized by type of laboratory test. In addition, National Cancer Institute-Common Terminology Criteria for Adverse Events (NCI-CTCAE) grades will be used in the summary of laboratory data. A listing of subjects with postbaseline abnormal laboratory results based on NCI-CTCAE grades will also be provided. Descriptive statistics will be calculated for each laboratory item at baseline and for observed values and changes from baseline at each scheduled point in time. Changes from baseline results will be presented in pre- versus posttreatment cross-tabulations (with classes for below, within, and above normal ranges) at selected points in time. Listings of subjects with any laboratory results outside the reference ranges or any markedly abnormal laboratory results will be provided.

Vital Signs

Descriptive statistics of pulse/heart rate and blood pressure (systolic and diastolic) values and changes from baseline will be summarized at each scheduled time point. The percentage of subjects with values beyond clinically important limits (specified in the SAP) will be summarized.

Physical Examination

Physical examination findings will be summarized at each scheduled time point. Descriptive statistics will be calculated at baseline and for observed values and changes from baseline at each scheduled time point. Frequency tabulations of the abnormalities will be made.

11.8. Other Analyses

Stratified Newcombe confidence limits for the common proportion difference with respect to the primary endpoint will also be provided by using the method of Yan and Su ([Yan und Su 2010](#)).

In addition, the primary endpoint will also be analyzed without adjustment for disease duration ('unadjusted analysis'). The two-group large-sample normal approximation Z-test ('asymptotic

Wald test of noninferiority') along with the two-sided 90% Wald type and Newcombe confidence interval will be computed.

For binary endpoints in Study Part 2 counts and percentage of subjects per treatment group along with odds ratio (OR), relative risk (RR) and risk difference (RD), two-sided 90% confidence intervals and p-values for treatment comparison based on Mantel-Haenszel weights adjusted for disease duration will be provided.

The change from baseline of continuous endpoints in Study Part 2 will be analyzed by an analysis of covariance model (ANCOVA) with the fixed effect factors for treatment group and disease duration and the baseline value as covariate. The Least-Squares means (LS means), the LS mean difference and the standardized mean difference (computed according to Hedges' g) with the two-sided 90% CI will be provided from the ANCOVA model.

Statistical analyses for time to event endpoints in Study Part 2 will provide the median time-to-even estimates per treatment group with two-sided 90% confidence intervals and the hazard ratio (including two-sided 90% confidence interval) calculated from Cox-regression with the factors treatment group and disease duration as covariate.

Exploration of possible heterogeneity of treatment effects across centers for the primary endpoint will be performed by descriptive frequency statistics including graphical display of the results of the individual centers, as appropriate. No pooling of centers will be performed.

11.9. Statistical Analyses per Study Part

Statistical analyses will be performed for each Study Part.

The confirmatory analysis is planned to be performed at the end of Study Part 2, ie, after all subjects have completed their visit at week 68 (ie, 40 weeks after randomization) or discontinued earlier. This analysis will include the confirmatory analysis of the primary endpoint, and the exploratory analyses of the major secondary endpoints and all other predefined efficacy and safety analyses from week 28 until week 68.

The analyses of Study Part 1 and Study Part 3 will be exploratory. The exploratory analysis of Study Part 1 will occur after all subjects have completed their visit at week 28 (ie, 28 weeks after study inclusion) or discontinued earlier. This analysis will include the safety analysis and all efficacy measures after week 0 and will cover the time until the week 28 visit. The exploratory analyses of Study Part 3 will occur after all subjects have completed their visit at week 116 (ie, 48 weeks after inclusion in Study Part 3 at week 68) or week 144 in case of subjects entering the re-treatment arm in week 116, at week 164 (ie, 96 weeks after inclusion in Study Part 3 at week 68) and at week 220 (ie, 152 weeks after inclusion in Study Part 3 at week 68), or week 248 in case of subjects entering the re-treatment arm in week 220 or discontinued earlier.

These analyses will include the safety evaluations and all efficacy measures after week 68, and will cover the time until week 116/164/220 and until week 144/192/248, respectively.

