Subjects with a PASI score=0 at weeks 20 and 28 will be defined as SRe and randomly assigned to the following two treatment groups: 2a) guselkumab 100 mg q8w or 2b) guselkumab 100 mg q16w. In addition, subjects with disease duration ≤ 2 years will be equally distributed to either group. Study visits of Study Part 2 will be conducted every 8 weeks.

To blind the study, study treatment (guselkumab or Placebo) will be administered q8w starting at week 28 until the end of study therapy (last administration in week 60). The q16w group will receive Placebo at weeks 28, 44 and 60. Subjects losing control of disease, defined as PASI score >5 at any visit during Study Part 2 (ie, until week 60), will enter the Re-treatment arm (group 2d, see section Re-treatment below).

The assessment for the primary endpoint (EP) will be at week 68 for both study groups.

In case of PASI <3 at week 68 the subject will not receive any study medication and enter the drug withdrawal part (Study Part 3). In case of PASI ≥ 3 at visit week 68 the subject will enter the re-treatment arm **3c** (see section Re-treatment below).

In case of PASI score >0 at the weeks 20 and/or 28 the subjects will continue to receive guselkumab 100 mg q8w until week 60 (last administration at week 60 visit) with final study assessments at week 68 and final safety follow-up visit at week 72 (defined as study group **2c**). At visit week 68 (for group **2c**), the investigator may continue treatment with commercially available guselkumab (ie, not provided by the Sponsor) to maintain a q8w interval. Due to the half-life of guselkumab, it is recommended not to start a new therapy during safety follow-up period (ie, 12 weeks after last dose). If the investigator feels strongly that an additional therapy is needed, this should be discussed with the sponsor before initiation of the new therapy.

Study Part 3: Week 68 through Week 220:

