3.2. Study Design Rationale

Dose rationale

A dose regimen of guselkumab 100 mg at weeks 0, 4 and q8w thereafter was selected for Study Part 1. This is the dose regimen, which is known to result in clinically meaningful improvement of the disease (SmPC TREMFYA®). In Study Part 2, subjects with a PASI score=0 at weeks 20 and 28 will be randomly assigned to either guselkumab 100 mg q8w or q16w to evaluate if these subjects maintain their disease control (absolute PASI score <3 at week 68) under extended dosing intervals. A larger dosing interval would provide higher comfort and better economy for subjects and physicians.

Duration of treatment period and whole study period

This study will have a 4-week screening phase, a 60-week treatment phase and a 12- to 160-week safety follow-up phase (depending on whether subjects are participating in Study Part 3). The duration of the regular subject's participation allows for an adequate treatment period and provides sufficient time to perform follow-up on safety and maintenance of response.

Blinding and randomization

Randomization will be used to minimize bias in the assignment of subjects to guselkumab 100 mg q8w or q16w (Study Part 2), to increase the likelihood that known and unknown subject attributes (eg, demographic and baseline characteristics) are evenly balanced across treatment groups, and to enhance the validity of statistical comparisons across treatment groups. Double-blinded treatment (Placebo treatment at weeks 28, 44 and 60 for subjects assigned to guselkumab 100 mg q16w) will be used to reduce potential bias during data collection and evaluation of the endpoints. Week 28 was chosen as the time for randomization because it allows subjects to reach steady-state

guselkumab concentrations with a q8w dosing regimen as well as steady-state clinical response. Randomization will be stratified by disease duration at baseline (≤ 2 years vs. >2 years) and by participation in the mechanistical substudy 1 to allow for evaluation of similarities or differences regarding the response rates.

Biomarker and DNA collection

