9.6. Safety Evaluations

Safety and tolerability of guselkumab will be monitored until 12 weeks after last administration of study drug by collecting information on AEs, including injection site and allergic reactions, clinical laboratory tests (hematology, chemistry and pregnancy testing), physical examinations, vital signs, concomitant medication review, and early detection of tuberculosis (TB), as specified in the TES. Subjects participating in Study Part 3 and not treated in the re-treatment arm will be monitored through week 220 by collecting information on AEs, including injection site and allergic reactions, vital signs, weight, and concomitant medication review. Any clinically significant abnormalities persisting at the end of the study/early withdrawal will be followed by the investigator until resolution or until a clinically stable endpoint is reached.

In cases of self-administration of SC study intervention at home, subjects are requested to contact their treating physician as soon as possible to consider reporting of an adverse event.

Clinical laboratory safety monitoring may be performed at a certified local laboratory identified by the study site rather than at the central laboratory; for selected measures (eg, urine pregnancy), home testing may be employed.

The study will include the following safety evaluations:

Adverse Events

AEs will be reported by the subject for the duration of the study. AEs will be followed by the investigator as specified in Section 12.

Injection Site Reactions

An injection site reaction (ISR) is any unfavorable or unintended sign that occurs at the study drug injection site. After administration of study drug at week 0, all subjects will be carefully observed at the study site for at least 30 minutes after the SC injection of study drug for symptoms of an ISR. If an ISR is observed, the subject should be treated at the investigator's discretion. Any adverse reaction (eg, pain, erythema, induration) should be noted on the AE page of the eCRF.

Allergic Reactions

Subjects must be observed carefully for symptoms of an allergic reaction (e.g., rash, urticaria, itching, shortness of breath, or drop in blood pressure) for at least 30 minutes after the study drug injection. If an allergic reaction is observed, treatment should be administered according to standard practice. Any allergic reaction should be noted on the AE page of the eCRF.

Clinical Laboratory Tests

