5.7. Safety Analyses

All safety analyses for the Re-treatment phase will be based on the Safety analysis set. Data from the safety follow-up at week R28 will be included in the analyses. Safety data, including but not limited to, adverse events (AEs), serious AEs, infections, serious infections, changes in laboratory assessments, and changes in vital signs, will be evaluated. Treatment-emergent AEs (TEAEs) will be summarized by Medical Dictionary for Regulatory Activities (MedDRA) system organ class (SOC) and Preferred Terms (PT).

For all continuous safety variables, descriptive statistics will include the N, mean, standard deviation, median, quartiles, minimum, and maximum. Categorical variables will be summarized using frequency counts and percentages. All tables will provide results by analysis group and overall.

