5.7. Safety Analyses

All safety analyses in Study Part 3 will be based on the Safety analysis set. Data from the safety follow-up at week 72 (study groups 2c and 3c) will not be included in the Study Part 3 analyses; last visit to be included for the Study Part 3 analyses is week 116/164/220 or R0 visit in case re-treatment was started. Safety data, including but not limited to, adverse events (AEs), serious AEs, infections, serious infections, and changes in vital signs, will be summarized by study group and overall. AEs will be summarized by Medical Dictionary for Regulatory Activities (MedDRA) system organ class (SOC) and Preferred Terms (PT) for each study group and overall.

For all continuous safety variables, descriptive statistics will include the N, mean, standard deviation, median, quartiles, minimum, and maximum. Categorical variables will be summarized using frequency counts and percentages.

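### The stated Part 2 safety window ends at week 68, four weeks before group 2c's planned follow-up ends, and a later, unplanned SAP recovers only the adverse events and deaths

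*Protocol*

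**What the plan says.** **Collection.** Protocol Section 9.6 states: "Safety and tolerability of guselkumab will be monitored until 12 weeks after last administration of study drug". For group 2c, the non-super-responders on open-label q8w treatment, Section 3.1 gives "last administration at week 60 visit", "with final study assessments at week 68 and final safety follow-up visit at week 72".

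**Planned analysis.** Section 11.9 runs the Part 2 analysis once every subject has completed week 68 or left earlier. It describes the content, beyond the primary and major secondary endpoints, as "all other predefined efficacy and safety analyses from week 28 until week 68". The synopsis says the same. Section 11.7 performs the safety analyses separately for each Study Part. Its adverse event rule takes in "All reported AEs with onset during the treatment phase", yet it also promises laboratory, vital-sign and examination summaries at every scheduled time point. Section 3.2 describes "a 60-week treatment phase and a 12- to 160-week safety follow-up phase", whereas Section 8 treats the active treatment phase as running from week 0 to week 68 for all subjects.

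**Supplied SAPs.**
- Part 3 SAP, Section 5.7: "Data from the safety follow-up at week 72 (study groups 2c and 3c) will not be included in the Study Part 3 analyses".
- Re-treatment SAP, Section 5.7: "Data from the safety follow-up at week R28 will be included in the analyses".
- Overall safety SAP (version 1.0, 11 April 2025), Sections 4.2 and 5.4.1: adverse events in all 822 subjects treated in Part 2 are analysed until 90 days after the last active dose. Section 6.2 says that the protocol did not plan this analysis, and Section 5.4.2 rules out any other safety parameter.

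**The concern.** Data are collected for 12 weeks after the last dose, but the analysis window stated for that Study Part closes after 8 of them. Super-responders who enter Part 3 have their adverse events after week 68 picked up by the Part 3 analysis. Group 2c has no Part 3, so for these subjects the planned Part 2 window is followed by nothing.

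Safety and tolerability in all study groups is a listed endpoint (Section 2.1.2). Section 11.7 measures it by the percentage of subjects with at least one occurrence of an event. Shortening the window can leave that percentage equal or lower, never higher. The stake is a Part 2 safety report for the largest treated group that does not match the follow-up which Section 9.6 commits to, and week 72 measurements with no identified place in the reporting.

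**Working it through.** **1. Reproduce the plan's follow-up visit.** Last dose at week 60 (Section 3.1) plus 12 weeks (Section 9.6) is week 72, the stated final safety visit for group 2c.

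**2. Part outside the stated window.** 72 − 68 = 4 weeks. That is 4/12 = 33% of the post-dose follow-up, and 4/(72 − 28) = 4/44 = 9% of weeks 28 to 72.

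**3. Who is affected.** The end of follow-up is the last dose week plus 12:

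| Last dose (week) | Follow-up ends (week) | Weeks beyond 68 |
|---|---|---|
| 28 | 40 | 0 |
| 36 | 48 | 0 |
| 44 | 56 | 0 |
| 52 | 64 | 0 |
| 60 | 72 | 4 |

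Only subjects dosed at week 60 have follow-up in the gap. The Overall safety SAP (Section 4.2) gives 525 subjects who continued in group 2c. Its counts agree with each other: 297 + 525 = 822 and 880 − 58 = 822. The number dosed at week 60 is not given, so 525 is an upper bound.

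**4. Exposure in the gap** (52.18 weeks per year):
- Upper bound: 525 × 4 / 52.18 = 40.2 subject-years.
- If 80% received the week 60 dose (an assumption): 420 × 4 / 52.18 = 32.2 subject-years.

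**5. Does the Overall safety SAP reach week 72?** With study day = 7 × week + 1, week 60 is day 421 and week 68 is day 477, both as in the Part 3 SAP's Table 2. Week 72 is day 505. The last dose plus 90 days is 421 + 90 = day 511. The 90-day window therefore contains the whole 84-day follow-up, for adverse events and deaths.

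**6. Comparison with re-treatment.** The last dose at R16 plus 12 weeks is R28. The structure is the same, but there the SAP includes the follow-up visit and summarises its laboratory and examination data (Sections 5.7.3.1 and 5.7.3.2). No reason is given for the different handling of week 72.

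**7. Part 1.** A subject who stops after the week 20 dose is followed to week 20 + 12 = 32, while the Part 1 analysis in Section 11.9 ends at the week 28 visit. The Overall safety SAP (Section 4.1) follows the 58 subjects who did not start Part 2 to the end of documentation, again for adverse events only.

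**The case against.** The case on the other side is substantial.

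- **The governing document is missing.** The Part 2 analysis has its own SAP, which was not supplied. The Part 3 exclusion partly follows from that analysis covering only groups 3a and 3b. This stands: whether the Part 2 SAP included week 72 cannot be checked.
- **Adverse events are covered.** The Overall safety SAP analyses adverse events, serious events, infections and deaths through week 72. Protocol Section 9.6 also sends clinically relevant laboratory, vital-sign and examination findings to adverse event reporting. This stands, and it means that important signals are not lost. What remains is the tabulation of week 72 values, and the fact that the recovery was not planned in the protocol.
- **The protocol can be read more widely.** Section 11.7 promises summaries at each scheduled time point for everyone dosed, and Section 11.11 brings in all available data. This stands as a conflict with Section 11.9 that needs reconciling. It does not show which section prevails.
- **Weeks 68 to 72 are not clean follow-up.** From week 68 the investigator may continue commercial guselkumab in group 2c (Section 3.1) or switch therapy (Section 6). This is a reason to flag such subjects, not to leave the period out.
- **No randomised comparison is involved.** Group 2c is open-label on the approved regimen, and the safety analysis is descriptive. This stands and limits the weight of the point.

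A reader might go further and infer from Sections 11.7 and 3.2 that all 12 post-dose weeks drop out: 525 × 12 / 52.18, about 121 subject-years, or 12/44 = 27% of weeks 28 to 72. The documents do not support this, because Section 8 extends the active treatment phase to week 68. They show only that the term is ambiguous.

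**Conclusion.** The stated Part 2 safety window falls 4 weeks short of the planned follow-up of group 2c. This is 33% of the post-dose follow-up and at most 525 subjects and about 40 subject-years, or about 32 if 80% received the week 60 dose. Section 11.9 is out of line with Section 9.6, with the time-point summaries in Section 11.7, and with the sponsor's own handling of R28.

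Three limits apply. Adverse events and deaths are recovered, although by an analysis added in April 2025. The absence of week 72 laboratory, vital-sign and examination summaries is established only for the three supplied SAPs. The schedule table is broken in the available text, so which tests fall at week 72 cannot be confirmed.

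A reader might conclude that post-treatment findings are never summarised. That is not supported: R28 data are summarised, clinically significant findings are to be captured as adverse events, and the Part 2 SAP has not been seen. Nor do the documents give an event rate from which to say how far incidence would be understated. The primary comparison is unaffected. This is an inconsistency that should be corrected, at small cost.

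**What to change.** 1. In Sections 11.9 and 11.7, define the Part 2 safety period as week 28 until 12 weeks after the last study drug administration, ending earlier at the start of re-treatment or entry into Part 3. Define the Part 1 period likewise for subjects who stop in Part 1.
2. Replace the treatment-phase wording of the adverse event rule in Section 11.7 with that period. This removes the conflict between the 60 weeks of Section 3.2 and the week 0 to 68 of Section 8.
3. Report the week 72 safety data of group 2c, including laboratory, vital-sign and examination data as far as collected, as an addendum to the Part 2 safety tables. Flag subjects who started commercial guselkumab or another therapy at or after week 68. If the Part 2 SAP already covered week 72, a cross-reference is enough.

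The efficacy cut at week 68 can stay. The supplied SAPs state that Part 2 has already been analysed, so an addendum is the only practical route. The cost is the wording and one set of descriptive tables. The drawback is that some data from weeks 68 to 72 were collected under non-study treatment.
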